### **Body weight**

The body weight endpoints will be analysed using a similar model as described for the primary endpoint except that the body weight at baseline will be included as a covariate and the analysis will be made on the original scale. Consequently, treatment means (LSMeans) and treatment differences will be presented with 95% CIs.

Body weight endpoints will be summarised using descriptive statistics and presented graphically.

### **Diabetes complications, eye examination and physical examination**

The eGFR endpoint will be log-transformed and analysed using normal linear regression model with treatment, stratum and sex as fixed factors and age and baseline value as covariates. Treatment means (LSMeans) and treatment ratio for the back-transformed results will be presented with 95% CIs. The analysis will not account for missing data.

All endpoints will be summarised. The endpoints for eGFR will be presented graphically.

### **Laboratory safety variables (haematology, biochemistry, coagulation, lipids, IgE, urine dipsticks, cytokine panel and hormones)**

The laboratory safety variables will be flagged if outside the reference range and abnormal values will be listed.

All endpoints for the laboratory safety variables will be summarised and the numerical variables will be presented graphically.

The endpoints for amylase and lipase will be analysed using a similar model as described for the primary endpoint except that the corresponding value at baseline will be included as a covariate. The individual values will be log-transformed prior to analysis, i.e. the change will be calculated on the log-transformed data and the log-transformed value at baseline will be included as a covariate.

The endpoints for TSH, IgE and cytokine panel will be analysed using a similar model as described for the primary endpoint except that the corresponding value at baseline will be included as a covariate and the analysis will be made on the original scale. Consequently, treatment means (LSMeans) and treatment differences will be presented with 95% CIs. If the model assumptions are not fulfilled then transformations of the data will be considered, e.g. the change will be calculated on the log-transformed data and the log-transformed value at baseline will be included as a covariate.

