#### 6.6 Withdrawal criteria

The subject may withdraw at will at any time. The subject may be withdrawn from the trial at the discretion of the investigator due to a safety concern or if judged non-compliant with trial procedures. Furthermore Novo Nordisk may decide to stop the trial, part of the trial or a trial site at any time.

The subject must be withdrawn if the following applies:

- 1. Included in the trial in violation of the inclusion and/or exclusion criteria and/or randomised in violation of the randomisation criteria
- 2. Participation in another clinical trial throughout the trial
- 3. If 2 consecutive NNC0114-0006 doses are missed
- 4. Subjects switching to an insulin pump at any time point during trial participation
- 5. If, during the trial, the randomised liraglutide/ liraglutide placebo dose of 1.2 mg/day or corresponding placebo volume after dose escalation is not tolerated
- 6. Hypoglycaemia and/or hyperglycaemia with ketosis during the treatment period posing a safety concern, as judged by the investigator
- 7. Acute pancreatitis. Subjects that are diagnosed with acute pancreatitis during the trial (as a minimum 2 of the following diagnostic criteria)
  - 1. Severe acute upper abdominal pain,
  - 2. Amylase and/or lipase >3x UNL or
  - 3. Characteristic findings on ultrasound/computerised axial tomography (CT)/magnetic resonance imaging (MRI)
- 8. Initiation of any prohibited medication (see Section 5.3.4).
- 9. Calcitonin  $\geq$  50 ng/l before week 54
- 10. Pregnancy
- 11. Intention of becoming pregnant
- 12. Unintended weight loss before week 54 posing a safety issue as judged by the investigator
- 13. Acute EBV or CMV infection before week 54 confirmed by central laboratory
- 14. Hepatitis B infection before week 54 confirmed by central laboratory

If a subject is withdrawn from the trial please see Section 8.1.7 for which visits the subject should attend.

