# 8.5.2.11 Virus screen for Epstein-Barr virus

Blood samples will be drawn according to Section  $\underline{2}$  for assessment of:

- IgM EBV antibodies
- IgG EBV nuclear antigen

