# 8.5.2.12 Virus screen for cytomegalovirus infection

The following will be analysed according to Section  $\underline{2}$ :

Date: Version: Status: Page: 07 May 2015 2.0 Final 76 of 141

- CMV IgM
- CMV IgG

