#### Trial specific AEs.

Severe infections should be reported as SAEs (i.e. should be reported as an "important medical event", if not fulfilling other SAE criteria like "hospitalisation").

Any infection requiring hospitalisation and/or which based upon appropriate medical judgement, is considered to be:

- i. More severe, longer-lasting or harder-to-treat than generally expected (e.g. for ear infections, pneumonia, meningitis, bronchitis, sinusitis or skin infections)
- ii. An infection with unusual localization
- Re-activation of a latent infection (e.g. JC polyomavirus (progressive multifocal leukoencephalopathy), Epstein-Barr virus, varicella-zoster virus (herpes zoster), herpes-simplex virus)
- iv. An opportunistic infection defined as an infection caused by an organism that does not normally cause disease but may occur in people with weakened immune systems. These micro-organisms may (but not exclusively) include:
  - Acinetobacter baumanni
  - Aspergillus sp.
  - Blastoschizomyces capitatus
  - Candida albicans
  - Clostridium difficile
  - Cryptococcus neoformans
  - Cryptosporidium
  - Cytomegalovirus

- Geomyces destructans
- Histoplasma capsulatum
- Isospora belli
- Kaposi's Sarcoma caused by Human herpesvirus 8 (HHV8), also called Kaposi's sarcoma-associated herpesvirus (KSHV)
- Legionnaires' Disease (Legionella pneumophila)
- Microsporidium
- Mycobacterium Tuberculosis
- Mycobacterium avium complex (MAC) (Nontuberculosis Mycobacterium)
- Pneumocystis jirovecii, previously known as Pneumocystis carinii f. hominis
- Pseudomonas aeruginosa
- Staphylococcus aureus
- Streptococcus pneumoniae
- Streptococcus pyogenes
- Trichosporon beigelii
- Toxoplasma gondii

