## 2.3 Section 5.3.1 NNC0114-0006

NNC0114-0006 C 100 mg/ml and NNC0114-0006 C 0 mg/ml will be administered as an i.v. infusion every 6 weeks (first administration Week 0 and last administration Week 48) at the trial sites. The i.v. infusion of NNC0114-0006 C 100 mg/ml or NNC0114-0006 C 0 mg/ml will be administered according to instructions as detailed in the Trial Materials Manual (TMM). Subjects will remain at the clinical trial site for at least 2 hours after completion of NNC0114-0006 C 100 mg/ml administration to be observed for AEs. On days with MMTT the administration of NNC0114-0006/placebo, may be done during the MMTT.

It must be confirmed by the investigator that infection parameters for Epstein-Barr, cytomegalovirus and hepatitis B (i.e. IgM EBV antibodies, IgG EBV nuclear antigen, CMV IgM, CMV IgG, HBcAB, HBsAb, HBsAg) have been accessed prior each infusion.

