### **Supportive secondary safety endpoints**

- Number of treatment emergent adverse events reported
  - from first dose of trial product to week 54
  - from week 54 to week 80
- Number of treatment emergent hyperglycaemic episodes
  - from first dose of trial product to week 54
  - from week 54 to week 80
- Number of treatment emergent episodes of diabetic ketoacidosis (DKA)
  - from first dose of trial product to week 54\*
  - from week 54 to week 80
- Number of subjects experiencing treatment emergent injection/infusion site reactions from first dose of trial product and during treatment period (54 weeks) caused by:
  - NNC0114-0006/liraglutide/placebo injection/infusion
- Number of treatment emergent hypoglycaemic episodes according to the American Diabetes Association (ADA) and Novo Nordisk definitions
  - from first dose of trial product to week 54\*
  - from week 54 to week 80
- Change in body weight from baseline to week 54 and week 80
- Diabetes complications (retinopathy and estimated glomeruli filtration rate) from baseline to week 54 and week 80
- Change in laboratory safety variables (haematology, biochemistry, coagulation, lipids, IgE, urine dipsticks, cytokine panel, and hormones), vital signs, electrocardiograms (ECGs), eye-examination and outcome of physical examination from baseline to week 54 and week 80
- Change in anti-NNC0114-0006 antibodies from baseline to week 54 and week 80
- Change in anti-liraglutide antibodies from baseline to week 54 and week 80

\* Key supportive secondary endpoint prospectively selected for disclosure (e.g. clinicaltrials.gov and EudraCT)

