### **2.4.1.2 Safety endpoints**

#### **Adverse events, DKA episodes and infusion/injection site reactions**

All adverse events (including DKA episodes and infusion/injection site reactions) will be coded using the latest version of Medical Dictionary for Regulatory Activities (MedDRA). An adverse event will be defined as treatment emergent if the onset of the adverse event occurs on or after the first day of trial product administration.

Treatment emergent adverse events will be summarised by system organ class, preferred term, seriousness, severity and relation to trial product. Separate summaries will be made for treatment emergent DKA episodes and for treatment emergent infusion/injection site reactions. The summaries will be made for the treatment period, for the observation period and for the entire trial period.

Additional information will be recorded on special eCRF pages for selected adverse events. This information will be listed.

All adverse events will be listed and separate listings will be made for DKA episodes and infusion/injection site reactions.

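### EBV, CMV and hepatitis B serology from nine post-baseline visits has no planned summary, so conversions not judged clinically significant are never tabulated by arm

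*SAP*

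**What the plan says.** **Collection.** Protocol Sections 8.5.2.9, 8.5.2.11 and 8.5.2.12 place the hepatitis B, EBV and CMV assays among the laboratory assessments for safety. The markers are "IgM EBV antibodies" and EBV nuclear antigen IgG, CMV IgM and IgG (under the heading "Virus screen for cytomegalovirus infection"), and HBcAb, HBsAb and HBsAg. Both flow charts schedule them at Visit 1 and then at Visits 10, 16, 23, 29, 35, 41, 47, 53 and 63.

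**Stated use.** Protocol Amendment 3, in its change to Section 5.3.1, says "It must be confirmed by the investigator that infection parameters for Epstein-Barr, cytomegalovirus and hepatitis B" have been accessed before each infusion. Withdrawal criterion 13 in Section 6.6 is "Acute EBV or CMV infection before week 54 confirmed by central laboratory". Criterion 14 is the equivalent for hepatitis B.

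**Analysis.** The safety endpoint in SAP Section 1.1.2.2 is "Change in laboratory safety variables (haematology, biochemistry, coagulation, lipids, IgE, urine dipsticks, cytokine panel, and hormones", and protocol Section 4.2.2.2 has the same list. SAP Section 2.4.1.2 analyses "Laboratory safety variables (haematology, biochemistry, coagulation, lipids, IgE, urine dipsticks, cytokine panel and hormones". Viral serology is in none of these, and SAP Section 3, which lists changes to the planned analyses, does not add it. For adverse events the SAP plans summaries by system organ class and preferred term, and then: "Separate summaries will be made for treatment emergent DKA episodes and for treatment emergent infusion/injection site reactions". Viral infection gets no separate summary.

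**The concern.** NNC0114-0006 neutralises IL-21. Protocol Section 18.1 names severe and opportunistic infections among its theoretical risks and reports a tendency towards more mild infections than on placebo in completed trials. Section 12.1 lists "Re-activation of a latent infection" among the infections under its severe-infection rules, with EBV as an example, and includes cytomegalovirus among the opportunistic organisms.

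The serology is objective, read at a central laboratory, and repeated on a fixed schedule in all four arms. Without a planned summary, the by-arm evidence on these viruses depends on which results investigators judge clinically significant and report. A new IgM or a seroconversion without symptoms may never be counted. Positivity and conversion rules chosen after the sponsor is unblinded at the additional database lock (SAP Section 2.4.2) would also be open to the criticism that the data drove them.

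**Working it through.** The plan gives no rate, sample size or power for viral serology, so there is no figure of its own to reproduce. The check is a count of visits, a comparison of lists, and the information that a table would carry.

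**1. Visits (protocol flow charts).**
- Visits 1 to 37: V10 (week 4), V16 (week 9), V23 (week 16), V29 (week 22), V35 (week 28), which is 5.
- Visits 38 to 90: V41 (week 34), V47 (week 40), V53 (week 46), V63 (week 54), which is 4.
- Total 5 + 4 = 9 post-baseline visits, none after week 54.
- Infusions after the first fall at weeks 6, 12, 18, 24, 30, 36, 42 and 48. Eight of the nine draws come two to three weeks before one of these, and the ninth is at the end of treatment.

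**2. Collected against analysed (protocol Section 8.5.2 against the SAP).**

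| Safety laboratory assessment | Repeated after baseline | Planned summary |
|---|---|---|
| Haematology, biochemistry, coagulation, lipids, IgE, dipstick, cytokines, hormones | Yes | Yes, SAP 2.4.1.2 |
| Anti-drug antibodies | Yes | Yes, own heading in SAP 2.4.1.2 |
| Hepatitis C, tuberculosis, HIV | No, Visit 1 only | None needed |
| EBV, CMV, hepatitis B | Yes, nine visits | None |

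Pregnancy testing aside, viral serology is the only repeatedly scheduled safety assay with no reporting plan.

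**3. Baseline status.** There is no draw at Visit 2 or 3, so under the SAP's baseline rule (Section 2) the Visit 1 sample is baseline. Exclusion criteria 15, 20 and 22 remove subjects positive for CMV IgM, for HBsAg or HBcAb, and for EBV IgM. Eligible subjects are therefore negative on these four markers at entry, and a later positive is new. No such exclusion applies to EBV nuclear antigen IgG or CMV IgG.

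**4. What zero events would show.** The one-sided 95% upper limit for 0 events in n subjects is 1 − 0.05^(1/n). The protocol plans 304 subjects at 1:1:1:1, so 304/4 = 76 per arm and 2 × 76 = 152 on NNC0114-0006. With 240 expected completers the figures are 60 and 120.
- n = 76: 1 − 0.05^(1/76) = 3.9%
- n = 152: 1 − 0.05^(1/152) = 2.0%
- n = 60: 4.9%
- n = 120: 2.5%

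These hold for EBV IgM, CMV IgM, HBsAg and HBcAb only. For IgG conversion n is the number seronegative at baseline, which the documents do not give. If 10% to 50% were seronegative (an assumption), n would be about 8 to 38 per arm and the limit would run from about 31% down to about 8%.

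**5. Could the table support a test?** With assumed event rates p1 and p2, p̄ their mean, n per group and two-sided 5%, power is Φ{[|p2 − p1| − 1.96·√(2p̄(1 − p̄)/n)] / √([p1(1 − p1) + p2(1 − p2)]/n)}.
- 1% against 5%: 0.30 for 76 v 76, 0.53 for 152 v 152
- 2% against 10%: 0.55 and 0.84
- 5% against 15%: 0.54 and 0.83

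A descriptive table is the realistic aim.

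**The case against.** The documents already give these infections several routes into the report. Infection confirmed by the central laboratory before week 54 requires withdrawal, and the investigator must try to establish the reason, which is recorded on the end-of-trial form when obtained (protocol Sections 6.6 and 8.1.7). Investigators must review all laboratory results for adverse events and report clinically significant worsening (Section 8.5). The laboratory adverse event definition in Section 12.1 counts further investigation or closer follow-up as active management. Treatment-emergent events are summarised by system organ class as well as preferred term, so related terms are pooled. The assay's stated uses are eligibility, the check before infusion and withdrawal, and SAP Section 2 permits supplementary safety analyses.

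Most of this stands, and it rules out some stronger readings. A reader might infer that laboratory-detected infection is never compared by arm, or is not reported at all. The adverse event and withdrawal routes contradict that. A reader might also infer that the serology is drawn because the antibody is thought to reactivate latent virus. No passage says so: Section 18.1 does not mention reactivation, which appears only as a reporting category in Section 12.1. Nor does the earlier tendency to mild infections show that these assays measure that harm, since nothing links it to EBV, CMV or hepatitis B.

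Two things survive the objection. A conversion judged not clinically significant has no route to a by-arm table, and permission to add analyses commits the sponsor to none.

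**Conclusion.** The concern holds in a limited form. Serology from nine post-baseline visits is in no endpoint list and no SAP summary. Infection found by the laboratory reaches the report only as an adverse event or as a criterion 13 or 14 withdrawal, and other conversions are not tabulated by arm.

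This is an omission in safety reporting. It does not bias the primary analysis or any safety analysis already listed. The documents give no expected conversion rate, so the number of cases that would go uncounted cannot be estimated. What can be sized is the information forgone: upper limits of 3.9% (76 subjects) and 2.0% (152) if no events occur, or 4.9% and 2.5% on expected completers. These assume entry criteria were applied as written and every counted subject has post-baseline samples. It would be wrong to extend them to IgG conversion, where the seronegative denominator is unknown.

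**What to change.** In SAP Section 2.4.1.2, add EBV, CMV and hepatitis B serology to the laboratory safety variables as a descriptive summary by arm on the safety analysis set, specified before the unblinding at the additional database lock:

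- the number and percentage of baseline-negative subjects with any post-baseline positive EBV IgM, CMV IgM, HBsAg or HBcAb, including samples that led to withdrawal;
- EBV nuclear antigen IgG and CMV IgG conversion, reported separately with the number seronegative at baseline shown for each arm;
- the number of withdrawals under criteria 13 and 14;
- a listing of cases with their linked adverse events.

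The endpoint list in SAP Section 1.1.2.2 should be aligned and the addition recorded in SAP Section 3. The cost is the SAP wording and the programming of one or two tables and a listing. The samples are already scheduled, and no dosing, infusion or withdrawal rule changes.

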## Vital signs and ECG

The systolic blood pressure, diastolic blood pressure and pulse endpoints will be analysed using a similar model as described for the primary endpoint except that the corresponding value at baseline will be included as a covariate and the analysis will be made on the original scale. Consequently, treatment means (LSMeans) and treatment differences will be presented with 95% CIs.

All endpoints will be summarised. The numerical endpoints will be presented graphically.

## Anti-NNC0114-0006 antibodies and anti-liraglutide antibodies

All endpoints will be summarised and presented graphically.

### 2.4.1.3 Pharmacokinetic endpoints

The PK endpoints described in [Table 2–3](#) will be derived from the individual NNC0114-0006 concentration-time curves after the first dose and after the last dose of NNC0114-0006. Furthermore, the trough concentration prior to dosing and the concentration 1 hour after dosing will be determined for NNC0114-0006 and the liraglutide concentration will be determined for liraglutide at the visits specified in the protocol, Section 2.

**Table 2–3 Definition and calculation of PK endpoints**

Endpoint	Description	Calculation
$AUC_{\tau, NNC0114-0006}$	Area under the NNC0114-0006 concentration-time curve over a dosing interval at steady state (SS) (defined as after last dose)	
<math>AUC_{\tau, NNC0114-0006}</math> will be derived as the area under the concentration-time curve using the linear trapezoidal technique based on observed values and actual measurement times between 0 and 6 weeks (after the last dose).
 
Missing values will be imputed using linear interpolation, possibly using measurements after 6 weeks. If the end time of the interval (i.e. 6 weeks) is after the time of the last quantifiable concentration, <math>t_z</math>, and the terminal rate constant, <math>\lambda_z</math>, can be determined then <math>AUC_{\tau, NNC0114-0006}</math> will be derived as the sum of <math>AUC_{0-t_z, NNC0114-0006}</math> and <math>AUC_{t_z-6 \text{ weeks}, NNC0114-0006}</math>, where <math>AUC_{t_z-6 \text{ weeks}, NNC0114-0006}</math> will be approximated using estimated values from the linear regression model applied for estimation of <math>\lambda_z</math>. If <math>\lambda_z</math> cannot be determined, then <math>AUC_{0-t_z, NNC0114-0006}</math> will be used instead of <math>AUC_{\tau, NNC0114-0006}</math>.

Endpoint	Description	Calculation
$\lambda_z$	Terminal rate constant for NNC0114-0006 (this is not an endpoint but it is used for calculation of some endpoints)	The terminal rate constant $\lambda_z$ will be determined through linear regression with the logarithm to concentration as the response variable and actual measurement time as the explanatory variable. Valid observations from the terminal part of the curve, which is approximately linear, will be used for the determination.
$t_{1/2}$	Terminal serum half-life after last dose of NNC0114-0006	Calculated as $\log(2)/\lambda_z$
$V_{ss, NNC0114-0006}$	The apparent volume of distribution of NNC0114-0006 at steady-state	Calculated as $MRT_{NNC0114-0006} * CL_{SS, NNC0114-0006}$
$CL_{SS, NNC0114-0006}$	Clearance of NNC0114-0006 at steady state	Calculated as $dose/AUC_{\tau, NNC0114-0006}$
$MRT_{NNC0114-0006}$	The mean residence time of NNC0114-0006	Calculated as $MRT = \frac{AUMC_{\tau} + \tau * AUC_{\tau-\infty}}{AUC_{\tau}}$ where $AUC_{\tau-\infty} = AUC_{0-t_z} + AUC_{t_z-\infty} - AUC_{0-\tau}$ and $AUMC_{0-\tau} = \sum_{i=2}^n (t_i - t_{i-1})(t_i C_i + t_{i-1} C_{i-1})$
$R_{A, AUC, NNC0114-0006}$	Accumulation ratio of NNC114-0006 defined as $AUC_{48-54 \text{ weeks}}/AUC_{0-6 \text{ weeks}}$	$AUC_{48-56 \text{ weeks}}$ will be calculated as described for $AUC_{\tau, NNC0114-0006}$ .  $AUC_{0-6 \text{ weeks}}$ will be calculated using a similar approach except that extrapolation using $\lambda_z$ will not be made

The PK endpoints will be summarised using descriptive statistics. The PK data will be presented graphically.

#### 2.4.2 Interim analysis

No formal interim analysis has been planned. However, an internal Novo Nordisk analysis is to be conducted after global last patient last treatment (LPLT) (visit 63) to inform on future clinical trials. An additional database lock (DBL) will be performed, when all patients have completed the main phase of the trial, i.e. after LPLT at visit 63. After the additional DBL, Novo Nordisk will become unblinded, while the trial investigators and patients will remain blinded throughout the entire trial.

### 3 Changes to the statistical analyses planned in the protocol

The below changes are made prior to the randomisation code break at the interim database lock:

- Various minor changes in wording done for clarification.
- The end of the treatment period is changed from the day before the visit at week 54 to the date of the visit at week 54, to ensure that the observations at end of treatment (Visit 63) gets assigned to the treatment period.
- Due to the change in assessments between the two flowcharts, it has been added that in case an endpoint is assessed at visits other than baseline, week 6, 12, 18, 24, 30, 36, 42, 48, 54, 65, and 80, values from the other visits will not be included in the MMRM.
- Subjects in the full analysis set will contribute 'as randomised' and not 'as treated' as per the ITT principle.
- The definition of the PK analysis set has been updated to include randomised subjects following the flowchart for the first 80 randomised subjects only.
- The following paragraph has been re-written to specify that decisions on data that are not in scope for the interim database lock can be taken after randomisation code break.
  - Furthermore, the individual profiles for C-peptide and plasma glucose from the MMTT in the treatment phase will be examined prior to interim database lock to establish whether it is possible to calculate all endpoints. If samples that are important for the derivation of certain endpoints are missing, these endpoints will not be calculated and they will be excluded from the analysis. In these cases, the subjects, observations or endpoints to be excluded and the reason for their exclusion will be documented prior to interim database lock. Data that are not in scope for the interim database lock, including individual PK profiles, biomarkers, antibodies and all data from the observation period may be examined after the interim database lock but before the full database lock. In cases where observations or endpoints are excluded from these data, it will be documented prior to the full database lock, and clearly stated if a decision was taken after randomisation code break.
- Specification on how to derive the primary endpoint in case the MMTT is stopped before 4 hours for reasons that are not due to hyperglycaemia or hypoglycaemia has been added:
  - In case the MMTT is stopped before 4 hours for reasons that are not due to hyperglycaemia or hypoglycaemia, the remaining C-peptide concentrations will be set to lloq/2.
- The description of the stratification variable has been updated from non-fasting C-peptide measurement at screening to non-fasting peak C-peptide measurement during MMTT at Visit 2 in alignment with protocol amendment 2.
- In the analysis of the primary endpoint, it has been deleted, that the variance-covariance matrix may depend on treatment, if an assumption of equal variance-covariance matrix between treatments turns out not to be reasonable. Instead it has been included that a sensitivity analysis where the variance-covariance matrix depends on treatment will be added if an assumption of equal variance-covariance matrix between treatments turns out not to be reasonable.

- Update of the first sensitivity analysis to specify that it is the endpoints calculated from MMTT stopped before 4 hours due to hyperglycaemia or hypoglycaemia that are excluded from the analysis, and not all the data for that subject.
- Sensitivity analysis added where endpoints calculated from MMTT profile that includes imputed values is excluded.
- Sensitivity analysis added where endpoints calculated from the MMTT, where the date of the MMTT is more than one day after the last liraglutide dosing is excluded.
- In the analysis exploring the effect of the different biomarkers on primary endpoint, the description of the analysis for categorical biomarkers has been deleted, as all biomarkers are continuous.
- In the exploratory analysis that investigates a potential effect of the concentration of liraglutide on the primary endpoint, it has been specified that the liraglutide concentration should be measured at the date corresponding to the MMTT, and not just the visit corresponding to the MMTT. The specification is done as the MMTT can be re-scheduled within 1-10 days.
- In alignment with the endpoint description in Section [1.1.2.2](#), it is specified that the endpoint for total daily insulin dose is derived per kg body weight.
- As only the insulin doses prior to visit 3, 63 and 89 will be transferred from the eDiary (as per the trial data handling plan), the description of the endpoints has been updated, and the statistical analysis has been changed from a MMRM to a normal regression model:
  - The total daily insulin dose will be derived as the average of the doses reported on the three days prior to visit 3, 63 and 89.
  - The endpoints will be analysed using normal linear regression model for the endpoint with treatment, stratum and sex as fixed factors and age and baseline value as covariates. Treatment means (LSMeans) and treatment differences will be presented with 95% CIs. The analysis will not account for missing data. The number of insulin injections will be derived as the average of the reported number on the three days prior to visit 3, 63 and 89.
- As only the insulin doses prior to visit 3, 63 and 89 will be transferred from the eDiary, the calculation of the endpoint “The number of weeks the subject is off bolus insulin” is not derived based on the dose information in the eDiary as originally planned, but based on the question in the CRF “Has the subject stopped taking bolus insulin since last visit”.
- The following analysis has been deleted in alignment with standard in GLP-1 trials:
  - A normal linear mixed effect model will be fitted to the 7-point SMPG profile data at week 54. The model will include treatment, time-point, the interaction between treatment and time-point, sex and stratum as fixed factors, age as a covariate and subject as a random effect. The variance-covariance matrix will be unstructured and may depend on treatment if an assumption of equal variance-covariance matrix between treatments turn out not to be reasonable. From this model the treatment

differences at each time-point will be estimated and explored. The same analysis will be made using the 7-point SMPG profile data at week 80

- For the analysis of within-subject variability of the before breakfast SMPG, it has been deleted that the 95% CI will be calculated using the delta method. Furthermore it has been clarified that the analysis will not account for missing data.
- As eGFR is only assessed at visit 1, 63 and 89, the statistical analysis has been changed from a MMRM to a normal regression model. Furthermore, it has been specified that the analysis will be done for the log-transformed endpoint:
  - The eGFR endpoint will be log-transformed and analysed using normal linear regression model with treatment, stratum and sex as fixed factors and age and baseline value as covariates. Treatment means (LSMeans) and treatment ratio for the back-transformed results will be presented with 95% CIs. The analysis will not account for missing data.
- Added:
  - In addition to the endpoints listed in Section 1.1.2.1, the following binary endpoints are derived for all subjects at baseline, week 54 and week 80:
    - $HbA_{1c} < 7.0 \%$ .
    - $HbA_{1c} \leq 6.5 \%$ .

